10.2. Study Candidate Screening

Subjects' eligibility for the study will be assessed based on study Inclusion and Exclusion criteria listed in Section 8.2 and 8.3, respectively. Subjects who have provided informed

consent and who have been determined to not meet all eligibility requirements will be withdrawn.

10.3. Informed Consent

Written Informed Consent must be obtained for all patients who are potential study candidates. Study candidates will be asked to sign the Informed Consent form before any study-specific tests or procedures are performed.

- The context of the study must be fully explained to the patient and patients must be given an opportunity to ask questions and have those questions answered to their satisfaction.
- Study personnel should explain to each potential participant that even if he or she agrees to participate in the study and signs an informed consent form, further testing might demonstrate that he or she is not eligible for the study.
- Written informed consent must be recorded appropriately by means of the subject's dated signature.
- The consent process must be documented in the subject's medical chart.

Research study candidates in the State of California will also be provided with the California Experimental Patient's Bill of Rights.

Subjects using a BSC mobile app have the option of providing access to mobile app data at any time as part of the study.

10.4. Screening

Subjects undergo screening related procedures to determine eligibility for the study. If a subject fails to meet all the eligibility criteria, they will be withdrawn.

Note: Key Indications for Use include:

[figure not shown]
- Persistent leg, buttock or groin pain, with or without back pain, that was relieved by lumbar flexion
- Moderate spinal stenosis at one or two levels from L1-L5
- Persistently symptomatic with unsuccessful response to at least 6 months of conservative treatment

For full list of Indications, please consult the current IDS Instructions for Use

Opioid medications will be collected and any adverse event occurring after the subject is enrolled (i.e. signing the Informed Consent Form) will be documented.

Subjects who participated in PRESS registry and received a Superion IDS implant maybe transferred/enrolled.

Confidential

events then withdrawn from the study. Acute opioid pain medications may be taken.

Confidential

[figure not shown][figure not shown]
12.2. Electronic Questionnaires

Questionnaires in electronic form may be collected directly using an electronic data collection platform at the clinical site (e.g. iPad). After completion by the subject or a clinician, data from the electronic questionnaires are transmitted directly into the EDC system.

12.3. Study Assessments

Confidential

Confidential

12.4. Data Retention

The Principal Investigator or his/her designee or Investigational site will maintain all essential study documents and source documentation that support the data collected on the study subjects in compliance with applicable regulatory requirements.

The Principal Investigator or his/her designee will take measures to prevent accidental or premature destruction of these documents. If for any reason the Principal Investigator or his/her designee withdraws responsibility for maintaining these essential documents, custody must be transferred to an individual who will assume responsibility and BSC must receive written notification of this custodial change. Sites are required to inform Boston Scientific in writing where paper or electronic files are maintained in case files are stored off site and are not readily available.

13. Deviations

An Investigator must not make any changes or deviate from this protocol, except to protect the life and physical well-being of a subject in an emergency. An investigator shall notify the sponsor and the reviewing IRB/EC/REB, and the regulatory authority if applicable, of any deviation from the investigational plan to protect the life or physical well-being of a subject in an emergency, and those deviations which affect the scientific integrity of the clinical investigation. Such notice shall be given as soon as possible, but no later than 5 working days after the emergency occurred, or per prevailing local requirements, if sooner than 5 working days.

All deviations from the investigational plan, with the reason for the deviation and the date of occurrence, must be documented and reported to the sponsor using the EDC system. Sites may also be required to report deviations to the IRB/EC/REB, and/or the regulatory authority, per local guidelines and/or national/government regulations.

Deviations will be reviewed and evaluated on an ongoing basis and, as necessary, appropriate corrective and preventive actions (including regulatory authority and/or IRB/EC/REB notification, site re-training, or site discontinuation/termination) will be put into place by the sponsor.

The sponsor will not approve protocol waivers.

14. Compliance

14.1. Statement of Compliance

This clinical investigation is financed by the study sponsor. Before the investigational site can be “Authorized to Enroll,” the investigational site must enter into a Clinical Study Agreement with the sponsor that details the financing of the study as well as the rights and obligations of the investigational site and the investigator.

This study will be conducted in accordance with 21 CFR parts 50, 56, 54 and 814.82, European Medical Device Regulations, the spirit of EN ISO 14155: Clinical Investigation of

Medical Devices for Human Subjects – Good Clinical Practice, the relevant parts of the ICH Guidelines for Good Clinical Practices, ethical principles that have their origins in the Declaration of Helsinki, and pertinent individual country laws and regulations. The study shall not begin until the required approval/favorable opinion from the IRB/EC/REB and/or regulatory authority has been obtained, if appropriate. Also, the study shall not begin prior to issuance of the site Authorization to Enroll, as provided by the sponsor. Any additional requirements imposed by the IRB/EC/REB or regulatory authority shall be followed, if appropriate.

14.2. Investigator Responsibilities

The Principal Investigator of an investigational site is responsible for ensuring that the study is conducted in accordance with the Clinical Study Agreement, the clinical investigation plan, ISO 14155, ethical principles that have their origins in the Declaration of Helsinki, any conditions of approval imposed by the reviewing IRB/EC/REB, and prevailing local and/or country laws and/or regulations, whichever affords the greater protection to the subject.

The Principal Investigator's responsibilities include, but are not limited to, the following.

- Prior to beginning the study, sign the Clinical Study Agreement and comply with the Investigator responsibilities as described in such Agreement.
- Prior to beginning the study, sign the Protocol Signature page documenting his/her agreement to conduct the study in accordance with the protocol.
- Provide his/her qualifications and experience to assume responsibility for the proper conduct of the study and that of key members of the site team through up-to-date curriculum vitae or other relevant documentation and disclose potential conflicts of interest, including financial, that may interfere with the conduct of the clinical study or interpretation of results.
- Make no changes in or deviate from this protocol, except to protect the life and physical well-being of a subject in an emergency; document and explain any deviation from the approved protocol that occurred during the clinical investigation.
- Create and maintain source documents throughout the clinical study and ensure their availability with direct access during monitoring visits or audits; ensure that all clinical-investigation-related records are retained per requirements.
- Ensure the accuracy, completeness, legibility, and timeliness of the data reported to the sponsor in the CRFs and in all required reports.
- Record, report, and assess (seriousness and relationship to the device/procedure) every adverse event as applicable per the protocol and observed device deficiency.
- Report to sponsor, per the protocol requirements, all reportable events.
- Report to the IRB/EC/REB and regulatory authorities any SAEs and device deficiencies that could have led to a SADE and potential/USADE or UADE, if required by applicable

laws or regulations or this protocol or by the IRB/EC/REB, and supply BSC with any additional requested information related to the safety reporting of an event.

- Ensure devices are used in accordance with the Instructions for Use.
- Allow the sponsor to perform monitoring and auditing activities and be accessible to the clinical research monitor or auditor and respond to questions during monitoring visits or audit(s).
- Allow and support regulatory authorities and the IRB/EC/REB when performing auditing activities.
- Ensure that informed consent is obtained in accordance with applicable laws, this protocol and local IRB/EC/REB requirements.
- Provide adequate medical care to a subject during and after a subject's participation in a clinical study in the case of adverse events, as described in the Informed Consent Form (ICF).
- Inform the subject of the nature and possible cause of any adverse events experienced.
- As applicable, provide the subject with necessary information on the IDS system, treatment and follow-up instructions and care.
- Inform the subject of any new significant findings occurring during the clinical investigation, including the need for additional medical care that may be required.
- Provide the subject with well-defined procedures for possible emergency situations related to the clinical study and make the necessary arrangements for emergency treatment.
- Ensure that clinical medical records are clearly marked to indicate that the subject is enrolled in this clinical study.
- Ensure that, if appropriate, subjects enrolled in the clinical investigation are provided with some means of showing their participation in the clinical investigation, together with identification and compliance information for concomitant treatment measures (contact address and telephone numbers shall be provided).
- Inform, with the subject's approval or when required by national regulations, the subject's personal physician about the subject's participation in the clinical investigation.
- Make all reasonable efforts to ascertain the reason(s) for a subject's premature withdrawal from clinical investigation while fully respecting the subject's rights.
- Ensure that an adequate investigation site team and facilities exist and are maintained and documented during the clinical investigation.

All investigators will provide their qualifications and experience to assume responsibility for their delegated tasks through up-to-date curriculum vitae or other relevant documentation and disclose potential conflicts of interest, including financial, that may interfere with the conduct of the clinical study or interpretation of results.

14.3. Delegation of Responsibility

When specific tasks are delegated by an investigator, including but not limited to conducting the informed consent process, the Principal Investigator is responsible for providing appropriate training, are competent to perform the tasks they have been delegated and adequate supervision of those to whom tasks are delegated. Where there is a sub investigator at a site, the sub investigator should not be delegated the primary supervisory responsibility for the site. The investigator is accountable for regulatory violations resulting from failure to adequately supervise the conduct of the clinical study.

14.4. Institutional Review Board / Ethics Committee

The investigational site will obtain the written and dated approval/favorable opinion of the IRB/EC/REB for the clinical investigation before recruiting subjects and implementing all subsequent amendments, if required.

A copy of the written IRB/EC/REB approval of the protocol (or permission to conduct the study) and ICF, must be received by the sponsor before recruitment of subjects into the study and shipment of investigational product/equipment. Prior approval must also be obtained for other materials related to subject recruitment or which will be provided to the subject.

Any amendment to the protocol will require review and approval by the IRB/EC/REB before the changes are implemented to the study. All changes to the ICF will be IRB/EC/REB approved; a determination will be made regarding whether a new ICF needs to be obtained from participants who provided consent, using a previously approved ICF. Annual IRB/EC/REB approval and renewals will be obtained throughout the duration of the study as required by applicable local/country laws or regulations or IRB/EC/REB requirements. Copies of the study reports and the IRB/EC/REB continuance of approval must be provided to the sponsor.

14.5. Sponsor Responsibilities

All information and data sent to BSC concerning subjects or their participation in this study will be considered confidential by BSC and will be kept confidential in accordance with all applicable laws and regulations. Only authorized BSC personnel and/or a BSC representative including, but not limited to Contract Research Organization (CRO), will have access to this information. Authorized regulatory personnel have the right to inspect and copy all records pertinent to this study. Study data collected during this study may be used by BSC for the purposes of this study, publication, and to support future research and/or other business purposes, such as overseeing and improving the performance of its device, new medical research and proposals for developing new medical products and procedures. All data used in the analysis and reporting of this study or shared with a third-party researcher will be without identifiable reference to specific subjects.

Information received during the study will not be used to market to subjects; subject names will not be placed on any mailing lists or sold to anyone for marketing purposes.

15. Monitoring

Monitoring will be performed during the study to assess continued compliance with the protocol and applicable regulations. In addition, the clinical research monitor verifies that study records are adequately maintained, that data are reported in a satisfactory manner with respect to timeliness, adequacy, and accuracy, and that the Principal Investigator continues to have sufficient staff and facilities to conduct the study safely and effectively. The Principal Investigator/institution guarantees direct access to original source documents by BSC personnel, their designees, and appropriate regulatory authorities.

The sponsor will put a plan in place to document the specific monitoring requirements.

The study may also be subject to a quality assurance audit by BSC or its designees, as well as inspection by appropriate regulatory authorities. It is important that the Principal Investigator and relevant study personnel are available during on-site monitoring visits or audits and that sufficient time is devoted to the process.

16. Potential Risks and Benefits

16.1. Instructions for Use

Please refer to the Instructions for Use for an overview of anticipated adverse (device) effects, and risks associated to the commercial device(s).

16.2. Risks associated with Participation in the Clinical Study

The subject might find it difficult, uncomfortable, or tiresome to complete study visits, evaluate the device, and/or questionnaires.

16.3. Possible Interactions with Concomitant Medical Treatments

No possible interactions have been identified for use of the Superion ID System concomitant with any specific medications. However, there may be some risk that is unknown.

The Superion ID System is MRI Conditional. Patients may undergo MRI safely when conditions described in the Instructions for Use are followed.

16.4. Risk Minimization Actions

Additional risks may exist. Risks can be minimized through compliance with this protocol, performing procedures in the appropriate hospital environment, adherence to subject selection criteria, close monitoring of the subject's physiologic status during research procedures and/or follow-ups and by promptly supplying BSC with all pertinent information required by this protocol.

16.5. Anticipated Benefits

The potential clinical benefit of the Superion ID System is reduction in the symptoms of neurogenic claudication. Other benefits known to occur from this symptom relief are increased functionality and quality of life for the patient. They may also have decreased use of analgesics, including opioids.

16.6. Risk to Benefit Rationale

The risk evaluation for the Superion ID System determined that all hazards attributed to the Superion ID System and overall remaining residual risks after implementations of the required mitigations have been evaluated. Based on the risk evaluation results, the potential benefit provided by the Superion ID System to treat neurogenic intermittent claudication secondary to a diagnosis of moderate lumbar spinal stenosis outweighs the remaining

residual risk. As the overall residual risk meets BSN's criteria, the Superion ID System is acceptable for use in a clinical setting.

17. Safety Reporting

17.1. Reportable Events by investigational site to Boston Scientific

It is the responsibility of the investigator to assess and report to BSC any event which occurs in any of following categories:

- All Serious Adverse Events, regardless of relationship.
- All Device Deficiencies
- Device and/or procedure related non-serious adverse events
- New findings/updates in relation to already reported events

When possible, the medical diagnosis should be reported as the Event Term instead of individual symptoms.

If it is unclear whether or not an event fits one of the above categories, or if the event cannot be isolated from the device or procedure, it should be submitted as an adverse event and/or device deficiency.

Any reportable event, experienced by the study subject after informed consent, whether or prior to, during or subsequent to the procedure, must be recorded in the eCRF.

Underlying diseases and chronic conditions are not reported as AEs unless there is an increase in severity or frequency during the course of the investigation. Death should not be recorded as an AE but should only be reflected as an outcome of one (1) specific SAE (see Table 17.2-1 for AE definitions).

Refer to Instructions for Use for the known risks associated with the commercial device(s).

17.2. Definitions and Classification

Adverse event definitions are provided in Table 17.2-1. Administrative edits were made on the safety definitions from applicable regulations and guidance including (but not limited to) 21 CFR Part 812, ISO 14155 and EU MDR 2017/745 for clarification purposes.

Table 17.2-1: Safety Definitions

Term	Definition
Adverse Event (AE) Ref: ISO 14155 Ref: MDGC 2020-10/1	Any untoward medical occurrence, unintended disease or injury, or any untoward clinical signs (including an abnormal laboratory finding) in subjects, users or other persons, in the context of a clinical investigation, whether or not related to the study medical device and whether anticipated or unanticipated. NOTE 1: This includes events related to the study medical device or comparator. NOTE 2: This definition includes events related to the procedures involved. NOTE 3: For users or other persons, this definition is restricted to events related to the study medical device.

Table 17.2-1: Safety Definitions

Term	Definition
Adverse Device Effect (ADE) Ref: ISO 14155 Ref: MDGC 2020-10/1	Adverse event related to the use of the study medical device NOTE 1: This includes any adverse event resulting from insufficiencies or inadequacies in the instructions for use, the deployment, the implantation, the installation, the operation, or any malfunction of the study medical device. NOTE 2: This definition includes any event resulting from use error or from intentional misuse of the study medical device. NOTE 3: This includes 'comparator' if the comparator is a medical device.
Serious Adverse Event (SAE) Ref: ISO 14155 Ref: MDGC 2020-10/1	Adverse event that led to any of the following: a) death, b) serious deterioration in the health of the subject, users or other persons as defined by either: 1) a life-threatening illness or injury, or 2) a permanent impairment of a body structure or a body function, including chronic diseases, or 3) in-patient hospitalization or prolongation of existing hospitalization, or 4) medical or surgical intervention to prevent life-threatening illness or injury or permanent impairment to a body structure or a body function c) foetal distress, foetal death, or a congenital abnormality or birth defect including physical or mental impairment. NOTE 1: Planned hospitalization for a pre-existing condition, or a procedure required by the clinical investigational plan, without a serious deterioration in health, is not considered a serious adverse event.
Serious Adverse Device Effect (SADE) Ref: ISO 14155 Ref: MDGC 2020-10/1	Adverse device effect that has resulted in any of the consequences characteristic of a serious adverse event.
Unanticipated Adverse Device Effect (UADE) Ref: 21 CFR Part 812	Any serious adverse effect on health or safety or any life-threatening problem or death caused by, or associated with, a device, if that effect, problem, or death was not previously identified in nature, severity, or degree of incidence in the investigational plan or application (including a supplementary plan or application), or any other unanticipated serious problem associated with a device that relates to the rights, safety, or welfare of subjects.
Unanticipated Serious Adverse Device Effect (USADE) Ref: ISO 14155 Ref: MDGC 2020-10/1	Serious adverse device effect which by its nature, incidence, severity, or outcome has not been identified in the current risk assessment. NOTE 1: Anticipated serious adverse device effect (ASADE) is an effect which by its nature, incidence, severity or outcome has been identified in the risk assessment.
Device Deficiency Ref: ISO 14155	An inadequacy of a medical device related to its identity, quality, durability, reliability, usability, safety or performance. NOTE 1: Device deficiencies include malfunctions, use errors, and inadequacy in the information supplied by the manufacturer including labelling.

Table 17.2-1: Safety Definitions

Term	Definition
Ref: MDGC 2020-10/1	NOTE 2: This definition includes device deficiencies related to the device under study or the comparator.
The following definitions will be used for defining hospitalization or prolongation of hospitalization for SAE classification purposes:	
Hospitalizations	
Hospitalization does not include:
 
 • emergency room visit that does not result in in-patient admission Note: although an emergency room visit does not itself meet the definition for hospitalization, it may meet other serious criteria (e.g. medical or surgical intervention to prevent permanent impairment or damage) • elective and pre-planned treatment/surgery for a pre-existing condition that is documented in the subject's record at the time of consent/enrollment • admission for social reasons and/or respite care in the absence of any deterioration in the subject's general condition (e.g. subject is homeless, caregiver relief) • pre-planned, protocol-specified admission related to the clinical study (e.g. procedure required by protocol)
Prolongation of hospitalization	
In-patient admission to the hospital that is prolonged beyond the expected standard duration for the condition under treatment.
 
Note: new adverse events occurring during the hospitalization are evaluated to determine if they prolonged hospitalization or meet another SAE criteria.

NOTES:

1. Hospitalizations occurring for the purpose of performing a planned procedure as per routine care such as implant procedures, or follow-up visits, are not to be reported as a SAE. However, complications or adverse events that occur during the planned procedure should be reported as (S)AEs if they meet the protocol specified definitions.
2. Elective/planned hospitalization(s) need not be reported as an SAE. However, complications or adverse events that occur during an elective/planned hospitalization, should be reported as (S)AEs if they meet the protocol specified definitions.
3. In the event of subject death during the conduct of the study, efforts should be made to perform an autopsy.
4. Lack of efficacy/decreased therapeutic response should not be reported as AEs. Clinical sequelae, other than pain, that occur as a result of lack of efficacy/decreased therapeutic response should be reported as AEs.
5. Clinically significant worsening of the pattern of intensity or distribution of Baseline pain symptoms should be reported as an AE.
6. Device deficiencies, including, but not limited to device/lead migrations, which are not associated with an adverse clinical outcome should only be reported as device deficiencies. However, if a device deficiency precipitates an AE, the AE should be

reported in the *Adverse Event* eCRF and the device deficiency should be documented in the *Device Deficiency* eCRF.

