8.2. Inclusion Criteria

Subjects who meet all of the following criteria (see Table 8.2-1) may be given consideration for inclusion in this clinical investigation, provided no exclusion criterion (see Section 8.3) is met.

Table 8.2-1: Inclusion Criteria

Inclusion Criteria	IC3. Scheduled to receive or previously received a commercially approved Boston Scientific Indirect Decompression System, per local Instructions for Use (IFU) IC4. Signed a valid, IRB approved informed consent form
---------------------------	---

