8.3. Exclusion Criteria

Subjects who meet any one of the following criteria cannot be included in this study or will be excluded from this clinical study.

Table 8.3-1: Exclusion Criteria

Exclusion Criteria	EC1. Meets any contraindication in BSC Indirect Decompression Systems local IFUCurrently diagnosed with a cognitive impairment, or exhibits any characteristic, that would limit the ability to assess pain relief or to complete study assessments in the opinion of the investigator
---------------------------	--

9. Subject Accountability

9.1. *Point of Enrollment*

A subject will be considered enrolled in the study when the Informed Consent Form (ICF) is signed. A subject will be considered implanted when a Superion IDS is successfully implanted.

9.2. *Withdrawal*

All subjects enrolled in the clinical study (including those withdrawn from the clinical study or lost to follow-up) shall be accounted for and documented. If a subject is withdrawn from the clinical investigation, the reason(s) shall be reported. If such withdrawal is due to problems related to investigational device safety or performance, the investigator shall ask for the subject's permission to follow his/her status/condition outside of the clinical study.

While study withdrawal is discouraged, subjects may withdraw from the study at any time, with or without reason and without prejudice to further treatment. In all cases of withdrawal or discontinuation, the Investigator will make all reasonable efforts to determine the reason for the subject's withdrawal. Subjects may be discontinued from the study for various reasons, which may include:

- Withdrawal of consent
- A safety concern defined by the Principal Investigator and/or Boston Scientific Neuromodulation (e.g., adverse event)
- Study non-compliance
- Inadequate use of device that may impact study outcomes
- Subject did not meet inclusion criteria or met an exclusion criterion after signing informed consent
- Surgical intervention that affects the Superion Indirect Decompression System
- Lost to follow-up
- Death of the subject

If device implantation is unsuccessful, the subject will be followed for 2 weeks post-implantation attempt to assess for procedure related adverse events. If Superion IDS is explanted, the subject should be followed for 30 days post-explant to assess for related adverse events and withdrawn. Subjects that undergo a revision or replacement procedure may continue in the study.

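### The SAE exemption for pre-existing conditions is dated to consent, so in subjects already implanted by then, elective care for an implant complication on file can drop out of the safety rates

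*Combined protocol and SAP*

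**What the plan says.** The rule is spread over several places in the protocol.

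- **Table 17.2-1, Hospitalizations row.** The row is introduced with "The following definitions will be used for defining hospitalization or prolongation of hospitalization for SAE classification purposes". Among the things that are not a hospitalization it lists "elective and pre-planned treatment/surgery for a pre-existing condition that is documented in the subject's record at the time of consent/enrollment".
- **Table 17.2-1, NOTE 1 to the SAE definition.** Not considered an SAE: "Planned hospitalization for a pre-existing condition, or a procedure required by the clinical investigational plan, without a serious deterioration in health".
- **Numbered note 2 under the table.** Elective or planned admissions in general are excused from SAE reporting. The note refers neither to consent nor to a pre-existing condition. Complications that arise during such a stay remain reportable.
- **Section 17.1.** "Underlying diseases and chronic conditions are not reported as AEs unless there is an increase in severity or frequency during the course of the investigation". Recording covers "Any reportable event, experienced by the study subject after informed consent".
- **Section 9.1.** "A subject will be considered enrolled in the study when the Informed Consent Form (ICF) is signed".
- **Sections 8.2 and 10.4.** The inclusion criterion admits people scheduled for the implant and people who already have it. Section 10.4 adds: "Subjects who participated in PRESS registry and received a Superion IDS implant maybe transferred/enrolled".
- **Section 6.3.** The safety parameters are the rates of related non-serious AEs, of all SAEs and of unanticipated AEs, to the end of the study.

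The visible text does not define 'pre-existing' relative to the implant, and it does not exclude device- or procedure-related conditions from the exemption.

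**The concern.** A consent-dated exemption works when consent comes before the implant, because nothing on file at consent can have been caused by the device. It works less well for someone who consents with the implant already in place. Any complication found between the implant procedure and PRESS 2 consent is on file at consent, and read literally it is pre-existing. A planned revision or removal during PRESS 2 follow-up can then be treated as care for a pre-existing condition.

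At stake is the safety output of a study whose analysis is descriptive, so the event rates are themselves the result. The error would run one way, towards fewer related events. It would concern admissions that happen after consent, while the subject is under study.

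**Working it through.** The plan states no event rate or sample size calculation, so there is no figure to reproduce. The check is to follow one complication through the rules.

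**Previously implanted subject, complication on file at consent**

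1. *Stable complication, elective and pre-planned admission, no other seriousness criterion met.* The Hospitalizations row and NOTE 1 both exempt the admission, so it can be classified as not an SAE. The complication began before consent. If it is read as a chronic condition under Section 17.1 and has not worsened, it may not be an AE either.
2. *Complication worsens after consent.* Section 17.1 makes the worsening an AE. Whether the admission counts as a hospitalization is arguable: the row turns on what was documented at consent and is silent on worsening, while NOTE 1 lifts the exemption on serious deterioration.
3. *Surgery to prevent a life-threatening outcome or permanent impairment.* SAE criterion b)4 does not depend on hospitalization. It still applies to an adverse event recorded after consent.
4. *Urgent or unplanned surgery.* The exemption does not apply.
5. *New complication during the planned stay.* Reportable under note 2.

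The gap is clear in case 1, arguable in case 2 and absent in cases 3 to 5.

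**Newly implanted subject, same complication**

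The synopsis places Baseline up to 30 days after consent and the procedure up to 90 days after Baseline. Consent therefore precedes the implant, and no complication of it can be on file at consent. The complication is a new event and is reportable under Section 17.1 as device- or procedure-related. The consent-dated row cannot exempt the admission, but note 2, read literally, can.

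So the two groups differ clearly in whether the complication is recorded as an AE. They differ less certainly in whether the planned admission is an SAE.

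**Do other rules recover case 1?**

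- The Section 17.1 instruction for unclear or device-linked events sends them in as an AE and/or a device deficiency. It does not make the admission serious.
- Section 9.2 follows an explanted subject for 30 days and then withdraws them. The explant appears in subject disposition, not in the SAE rate.
- Criterion b)4 does not reach elective treatment of a stable complication that threatens neither life nor permanent impairment.

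**Size**

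Exempt admissions per 1,000 previously implanted subjects = 1,000 × c × a × x, where

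- c = share with a related complication on file at consent,
- a = share of those with a later planned admission for it,
- x = share of those admissions that fall in case 1.

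The documents give none of the three. Purely as an illustration, assume c from 2% to 8%, a from 25% to 50%, and x = 1:

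- low: 1,000 × 0.02 × 0.25 × 1 = 5
- high: 1,000 × 0.08 × 0.50 × 1 = 40

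Setting x = 1 makes each result a ceiling for its inputs, because it lets nothing through by worsening, serious deterioration or b)4. The effect on a pooled rate would also need the share of previously implanted subjects. Section 9.3 caps the study at 3,000 implanted subjects without splitting them, and its initial cap of 30 per site covers new implants only.

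**The case against.** The strongest reply is that the exemption is narrow and that several rules stand behind it. The care must be both elective and pre-planned. Only the hospitalization route to seriousness is closed. The wording does not settle whether the surgery itself, or only the condition, must be on record at consent; if the surgery must be, few subjects are affected. The Section 17.1 sentence speaks of underlying diseases and chronic conditions, and an implant complication need not be one. All of this stands. It limits the point to cases 1 and 2, and the unsettled wording is itself a source of inconsistent classification between sites.

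Three stronger readings are tempting, and the documents do not support them.

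- A reader might infer that planned surgery for such a complication is automatically not an SAE. Cases 3 to 5 show otherwise.
- A reader might infer that the same planned reoperation is an SAE in a new subject and exempt in a previously implanted one. Note 2 carries no consent date and could exempt the admission in both, so that contrast is not established.
- A reader might infer that the gap remains even if PRESS events are carried over. Section 17.1 also asks for updates to events already reported, so a later admission could be reportable as an update. The schedule for PRESS subjects (Table 10.1-2) is redacted, so carry-over cannot be checked either way and is not counted as an omission.

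**Conclusion.** The point holds in limited form. For subjects implanted before consent, the protocol's own wording allows a stable, device- or procedure-related complication on file at consent to be classed as pre-existing. It may then not be recorded as a new AE, and an elective, pre-planned admission for it can be classified as not an SAE unless there is serious deterioration or another seriousness criterion is met. The Section 6.3 rates can be understated as a result, in the device's favour.

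The conclusion rests on a literal reading of the Hospitalizations row and on the absence, in the visible text, of any carve-out for related conditions. The size is unknown. The 5 to 40 per 1,000 shown above depends wholly on assumed inputs and should not be read as an estimate or as a difference between the two groups.

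**What to change.** Make the same edit in four places: the Hospitalizations row, NOTE 1 to the SAE definition, numbered note 2 under Table 17.2-1, and the chronic-condition sentence of Section 17.1. State that:

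- a condition rated possibly, probably or causally related (the Table 17.3-1 categories) to the Superion device or its implant procedure is never pre-existing;
- the elective or planned exemption does not apply to an admission for such a condition;
- any such admission after consent is recorded and assessed against the SAE definition, with its relationship, whether the subject was implanted before or after consent.

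Moving the reference date from consent to implant would not be enough, because note 2 would still excuse the admission. It would also sweep in unrelated illnesses that began after the implant. Tying the carve-out to relatedness avoids both problems.

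Report the safety rates separately for newly and previously implanted subjects, so that any remaining difference in ascertainment is visible.

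The cost is a definitional edit in four places and one further split of the safety tables. For previously implanted subjects, sites would have to judge the relationship of a complication that began before consent, using PRESS or medical records. The reported SAE rate may rise slightly.
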